7.6.2.2. Reporting Other Special Situations

All other special situation reports must be reported on the special situations report form and forwarded to Gilead PVE within 24 hours of the investigator becoming aware of the situation. These reports must consist of situations that involve study IMP and/or Gilead concomitant medications, but do not apply to non-Gilead concomitant medications.

Special situations involving non-Gilead concomitant medications does not need to be reported on the special situations report form; however, for special situations that result in AEs due to a non-Gilead concomitant medication, the AE should be reported on the AE form.

Any inappropriate use of concomitant medications prohibited by this protocol should not be reported as “misuse,” but may be more appropriately documented as a protocol deviation.

Refer to Section 7.3 and the eCRF completion guidelines for full instructions on the mechanism of special situations reporting.

All clinical sequelae in relation to these special situation reports will be reported as AEs or SAEs at the same time using the AE eCRF and/or the SAE report form. Details of the symptoms and signs, clinical management, and outcome will be reported, when available.

8. STATISTICAL CONSIDERATIONS

8.1. Analysis Objectives and Endpoints

8.1.1. Analysis Objectives

The primary objective of this study is:

- To evaluate whether SEL can slow the decline in kidney function

The secondary objectives of this study are:

- To evaluate whether SEL can reduce the risk of kidney failure, or reduce the risk of death due to kidney disease in subjects with diabetic kidney disease (DKD)
- To assess the safety and tolerability of SEL in subjects with DKD

CCI

[REDACTED]

[REDACTED]

[REDACTED]

[REDACTED]

[REDACTED]

[REDACTED]

8.1.2. Primary Endpoint

The primary efficacy endpoint of this study is:

- eGFR_{cr} slope from treatment-specific baselines

8.2. Analysis Conventions

8.2.1. Analysis Sets

8.2.1.1. Efficacy Analysis Set

The final analysis set for efficacy analysis is the Intent-to-treat (ITT) Analysis Set, which includes all subjects who were randomized in the study.

8.2.1.2. Safety Analysis Set

The final analysis set for safety analyses is the Safety Analysis Set, which includes all subjects who receive at least one dose of study drug. All data collected during treatment will be included in the safety summaries.

CCI

CCI

8.2.1.4. Biomarker Analysis Set

The Biomarker Analysis Set will include data from subjects in the Safety Analysis Set who have the necessary baseline and on-study measurements to provide interpretable results for the specific parameters of interest.

8.3. Data Handling Conventions

Values for missing safety laboratory data will not be imputed. However, a missing baseline result will be replaced with a screening result, if available. If no pre-treatment laboratory value is available, the baseline value will be assumed to be normal (i.e, no grade [Grade 0]) for the summary of graded laboratory abnormalities. If safety laboratory results for a subject are missing for any reason at a time point, the subject will be excluded from the calculation of summary statistics for that time point.

Values for missing vital sign data will not be imputed. However, a missing baseline result will be replaced with a screening result, if available.

PK concentration values and PK parameter values below the limit of quantitation (BLQ) will be presented as “BLQ” in the data listings. BLQ values that occur prior to the first dose will be treated as 0, BLQ values at all other time points will be treated as 1/2 of the lower limit of quantitation (LLOQ).

Laboratory data that are continuous in nature but are less than the LLOQ or above the upper limit of quantitation will be imputed to the value of the lower or upper limit minus or plus one significant digit, respectively (e.g., if the result of a continuous laboratory test is < 20, a value of 19 will be assigned; if the result of a continuous laboratory test is < 20.0, a value of 19.9 will be assigned).

Procedures for handling missing data for eGFR will be described in the statistical analysis plan (SAP).

8.4. Demographic Data and Baseline Characteristics

Demographic and baseline measurements will be summarized by treatment group using standard descriptive statistics (n, mean, standard deviation [SD], median, 1st quartile [Q1], 3rd quartile [Q3], minimum, maximum for continuous variables and number and percentage of subjects for categorical variables) for the ITT Analysis Set.

Demographic summaries will include sex, race/ethnicity, and age.

Baseline characteristics may include eGFR, UACR, height, weight, BMI, concomitant use of SGLT-2 inhibitors, prior use of ACEi and/or ARB, and other variables of interest.

8.5. Efficacy Analysis

8.5.1. Primary Analysis

The Primary Analysis Set for efficacy analyses is the ITT Analysis Set, which includes all subjects who were randomized in the study.

8.5.1.1. Analysis of eGFR Slope

Definition of Baseline

Baseline eGFR_{cr} for the primary analysis is defined as below:

- SEL arm (Arm A): The average of the measurements at Visit C and Visit 1. This baseline will also be referred to as post-run-in baseline.
- Placebo arm (Arm B): The average of the measurements at Visit A (enrollment) and Visit B. This baseline will also be referred to as pre-run-in baseline.

The primary analysis of eGFR_{cr} slope will be performed after all subjects in the ITT Analysis Set complete the Week 48 visit or discontinue from the study. Pre-run-in baseline eGFR_{cr} and post-run-in baseline eGFR_{cr} will be used for the placebo and SEL arms, respectively. Baseline eGFR_{cr} as well as all on- and off-treatment eGFR_{cr} values collected after Visit 1 through time of the analysis for all subjects with available data will be included. eGFR_{cr} slope will be compared between SEL and placebo using a random slope model. The random slope model will have eGFR_{cr} values starting from Baseline as the outcome, and will include terms for pre-run-in baseline eGFR_{cr} as a continuous variable, pre-run-in baseline UACR category (< 1500 mg/g vs. ≥ 1500 mg/g), concomitant use of SGLT-2 inhibitors, treatment group, visit, and treatment-by-visit interaction. The difference in eGFR_{cr} slope between SEL and placebo groups will be estimated and tested.

8.5.2. Secondary Analyses

The Secondary Analysis Set for efficacy analyses is the ITT Analysis Set.

8.5.2.1. Analysis of proportion of Kidney Clinical Events at Week 48

Kidney Clinical Event is defined as any of the following events:

- Confirmed ≥ 40% decline in eGFR_{cr} from baseline, or
- Kidney failure (dialysis performed for at least 4 weeks, kidney transplantation, or confirmed decrease in eGFR_{cr} to < 15 mL/min/1.73 m² for subjects without dialysis or kidney transplantation), or
- Death due to kidney disease

The ≥ 40% decline in eGFR_{cr} from baseline and sustained decrease in eGFR_{cr} to < 15 mL/min/1.73 m² components need to be confirmed at the next scheduled visit but at least 4 weeks after the index measurement. Events of eGFR_{cr} < 15 mL/min/1.73 m² or eGFR_{cr} decline ≥ 40% from baseline without confirmation due to study discontinuation (e.g., death or lost to follow-up) will be included in the analysis.

The analysis of proportion of Kidney Clinical Events will be conducted when all subjects in the ITT Analysis Set reach Week 48 Visit or discontinue from the study. Number and proportion of subjects who experience a Kidney Clinical Event will be summarized. The Cochran-Mantel-Haenszel (CMH) approach adjusting for stratification factors will be used for hypothesis testing of Kidney Clinical Events.

Number and proportion of subjects who experienced each component of the Kidney Clinical Events will also be summarized.

8.5.2.2. Analysis of time from randomization to a Kidney Clinical Event

The $\geq 40\%$ decline in $eGFR_{cr}$ from baseline and sustained decrease in $eGFR_{cr}$ to < 15 mL/min/1.73 m² components need to be confirmed at the next scheduled visit but at least 4 weeks after the index measurement. Events of $eGFR_{cr} < 15$ mL/min/1.73 m² or $eGFR_{cr}$ decline $\geq 40\%$ from baseline without confirmation due to study discontinuation (e.g., death or lost to follow-up) will be included in the analysis. The date the first sample meets the threshold will be used as the date in the analysis.

If a subject has not experienced any Kidney Clinical Events at the time of global study end date/early discontinuation of the study, this subject will be censored at the time of the last assessment of kidney function.

The analysis of time from randomization to a Kidney Clinical Events will be conducted when all subjects in the ITT Analysis Set reach Week 48 or discontinue from the study. Baseline as well as all on- and off-treatment $eGFR_{cr}$ values collected after Visit 1 through the end of the study will be included in the evaluation of the endpoint. The comparison will be performed between the SEL and placebo arms using a stratified log-rank test, stratified by randomization stratification factors. Median survival times and 95% Confidence Intervals (CIs) for the SEL and placebo arms will be estimated using Kaplan-Meier method. Hazard ratio (HR) and 95% CI comparing the SEL and placebo arms will be estimated using a stratified Cox proportional hazard model, stratified by randomization stratification factors.

8.5.2.3. Analysis of $eGFR_{cys}$ slope from pre-run-in baseline

The analysis of $eGFR_{cys}$ slope from pre-run-in baseline will be performed after all subjects in the ITT Analysis Set complete the Week 48 visit or discontinue from the study. Pre-run-in baseline $eGFR_{cys}$ will be used for both placebo and SEL arms. Baseline $eGFR_{cys}$ as well as all on- and off-treatment $eGFR_{cys}$ values collected after Visit 1 through time of the analysis for all subjects with available data will be included. $eGFR_{cys}$ slope will be compared between SEL and placebo using a random slope model. The random slope model will have $eGFR_{cys}$ values starting from pre-run-in Baseline as outcome, and include terms for pre-run-in baseline $eGFR_{cys}$ as a continuous variable, pre-run-in baseline UACR category (< 1500 mg/g vs. ≥ 1500 mg/g), concomitant use of SGLT-2 inhibitors, treatment group, visit, and treatment-by-visit interaction. The difference in $eGFR_{cys}$ slope between SEL and placebo groups will be estimated and tested using the random slope model.

CCI

[REDACTED]

CCI

[Redacted]

[Redacted]

[Redacted]

[Redacted]

[Redacted]

[Redacted]

[Redacted]

[Redacted]

[Redacted]

CCI
[REDACTED]

[REDACTED]

[REDACTED]

[REDACTED]

[REDACTED]

[REDACTED]

[REDACTED]

[REDACTED]

[REDACTED]

8.5.4. Multiplicity Adjustment

The primary endpoint and each secondary endpoint will be evaluated at a one-sided Type 1 error level of 0.15. No formal multiplicity adjustment will be performed.

8.6. Safety Analysis

Safety will be assessed during the study through the reporting of AEs, and by clinical laboratory tests and vital sign assessments at various time points during the study. Concomitant medication usage will also be assessed throughout the study.

All safety data collected on or after the date that SEL or PTM was first dispensed up to the date of last dose of SEL or PTM plus 30 days, including data collected during the Run-in period, will be summarized by treatment group (according to the study drug received).

8.6.1. Extent of Exposure

A subject's extent of exposure will be generated from the study drug administration eCRF. Exposure data will be summarized by treatment group.

8.6.2. Adverse Events

Clinical and laboratory adverse events will be coded using the Medical Dictionary for Regulatory Activities (MedDRA). System Organ Class (SOC), High-Level Group Term (HLGT), High-Level Term (HLT), Preferred Term (PT), and Lower-Level Term (LLT) will be attached to the clinical database.

Events will be summarized on the basis of the date of onset for the event. Treatment-emergent adverse events (TEAEs) are defined as one or both of the following:

- Any AEs with an onset date on or after the study drug start date and no later than 30 days after permanent discontinuation of study drug
- Any AEs leading to premature discontinuation of study drug. Summaries (number and percentage of subjects) of TEAEs (by SOC, and PT) will be provided by treatment group. TEAEs will also be summarized by relationship to study drug and severity. In addition, TEAEs leading to premature discontinuation of study drug will be summarized and listed.

8.6.3. Laboratory Evaluations

Selected laboratory data (using conventional units) will be summarized using only observed data. Data and change from baseline at all scheduled time points will be summarized by treatment group and study visit.

Graded laboratory abnormalities will be defined using the grading scheme in CTCAE version 5.0 ([Appendix 4](#)).

Incidence of treatment-emergent laboratory abnormalities, defined as values that increase at least one toxicity grade from baseline at any time post baseline up to and including the date of last dose of study drug plus 30 days, will be summarized by treatment group.

8.6.4. Other Safety Evaluations

Vital sign measurements will be summarized by treatment arm and listed by subject.

CCI

[REDACTED]

[REDACTED] CCI [REDACTED]
[REDACTED]
[REDACTED]

CCI

[REDACTED]

[REDACTED]

8.9. Sample Size

8.9.1. Sample Size Determination

With a sample size of 300 subjects (150 per treatment arm), power to detect a difference in $eGFR_{cr}$ decline rate of 3.7 mL/min/1.73 m²/year (common SD = 10 mL/min/1.73 m²/year) between SEL 18 mg and placebo using a two-sample t-test is 99% at a 1-sided significance level of 0.15. Assuming 15% dropout, with a sample size of 254 (127 per arm), the power is 97%.

8.10. Data Monitoring Committee

An external multidisciplinary data monitoring committee (DMC) will review the progress of the study and perform interim reviews of safety data and provide recommendation to Gilead whether the nature, frequency, and severity of adverse effects associated with study drug warrant the early termination of the study in the best interests of the participants, whether the study should continue as planned, or the study should continue with modifications. The DMC may also provide recommendations as needed regarding study design.

The initial DMC meeting will occur after approximately 300 subjects reach Week 12 or discontinue from the study. Following this, subsequent meetings will occur approximately once every 6 months. The DMC's specific activities will be defined by a mutually agreed charter, which will define the DMC's membership, conduct and meeting schedule.

While the DMC will be asked to advise Gilead regarding future conduct of the study, including possible early study termination, Gilead retains final decision-making authority on all aspects of the study.

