Study Design:

[figure not shown]
This is a Phase 2b, randomized, double-blind, placebo-controlled, parallel group, multicenter study evaluating the efficacy and safety of SEL in subjects with type 2 diabetes mellitus (T2DM) and moderate to advanced DKD.

Following the screening period, eligible subjects will enroll into a Run-in period of at least 5 weeks. During the Run-in period, all subjects will receive placebo-to-match (PTM) for at least 7 consecutive days. Subsequently, all subjects will receive SEL (18 mg) for at least 4 weeks.

After completing the Run-in period, subjects eligible for randomization will be randomized in a 1:1 ratio to receive SEL (18 mg) or PTM, orally once daily. Randomization will be stratified by estimated glomerular filtration rate (eGFR), urine albumin to creatinine ratio (UACR), and concomitant use of sodium-glucose co-transporter-2 (SGLT-2) inhibitors.

Subjects will continue to receive SEL or PTM in a double-blind fashion until death, study drug discontinuation, kidney failure (dialysis performed for at least 4 weeks, kidney transplantation, or confirmed decrease in eGFR to $< 15 \text{ mL/min/1.73 m}^2$ for subjects without dialysis or kidney transplantation), or the global study end date.

Study Design Schema

Abbreviations: EOS = End of Study, EOT = End of Treatment, PTM = placebo to match, SEL = Selonsertib

- a Prior to randomization, subjects must have at least 7 consecutive daily doses of study drug immediately prior to Visit C and Randomization (Visit 1)
- b Post-run-in baseline eGFR is defined as the average of Visit C and Visit 1 eGFR values. Pre-run-in baseline is defined as the average of Visit A and Visit B eGFR values.
- c If kidney failure is reached, subjects should discontinue study drug and remain on study.
- d If a subject permanently discontinues study drug, there will be a 30 Day EOT Follow-up visit. Subjects who permanently discontinue study drug prior to the global study end date will have an EOT visit and a 30 Day (± 7 days) EOT Follow-up visit. Subjects are encouraged to complete all remaining study visits until the global study end date.
- e The global study end date will occur when the last randomized subject reaches 48 weeks and/or all subjects on study have completed end of study assessments and the 30 Day EOS Safety Follow-up visit.

Number of Subjects Planned: Approximately 300 randomized subjects

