Subjects who permanently discontinue study drug can have limited follow-up as defined in the schedule of procedures table, if requested. If full consent has not been withdrawn, subjects who permanently discontinue study drug and are no longer willing or able to attend clinic visits in-person will be asked to continue study participation via remote assessments. Subjects will be contacted approximately every 24 weeks until the global study end date. Subjects who have reached kidney failure will be followed via remote assessments as well.

The global study end date will occur when the last randomized subject reaches 48 weeks and/or all subjects on study have completed end of study assessments and the 30 Day EOS Safety Follow-up visit.

CCI

**Test Product, Dose,
and Mode of
Administration:**

SEL 18 mg or PTM to be taken orally once daily

**Criteria for
Evaluation:**

Safety:

The safety of SEL will be assessed during the study through the reporting of adverse events (AEs) and serious adverse events (SAEs), physical examinations (PEs), clinical laboratory tests, vital sign assessments, concomitant medications, and ECGs at various time points during the study.

A data monitoring committee (DMC) will meet regularly to evaluate all available safety data accumulated during the study. In addition, endpoints of interest (kidney and CV events) will be reviewed and adjudicated.

Statistical Methods:

Primary Efficacy Analyses

Analysis Methods

The primary analysis set for efficacy analyses is the ITT Analysis Set, which includes all subjects who were randomized in the study.

Definition of Baseline

Baseline eGFR_{cr} is defined as below for the primary analysis:

- SEL arm (Arm A): The average of the measurements at Visit C and Visit 1. This baseline will also be referred to as post-run-in baseline.
- Placebo arm (Arm B): The average of the measurements at Visit A (Enrollment) and Visit B. This baseline will also be referred to as pre-run-in baseline.

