2. TYPE OF PLANNED ANALYSIS

2.1. Interim Analyses

2.1.1. DMC Analysis

An external multidisciplinary Data Monitoring Committee (DMC) will review the progress of the study and perform interim reviews of the safety data in order to protect subject welfare and preserve study integrity. To ensure the best interests of the participants, the DMC will make recommendations to the sponsor if the nature, frequency, and severity of adverse effects associated with the study treatment warrant the early termination of the study, the continuation of the study, or the continuation of the study with modifications.

The initial review will be conducted after 300 randomized subjects have completed through Week 12 or discontinued from the study. Additional meetings will be scheduled approximately every 6 months.

The DMC's role and responsibilities and the scope of analysis to be provided to the DMC are provided in a mutually agreed upon charter, which defines the DMC membership, meeting logistics, and meeting frequency.

No formal interim efficacy analysis, which may lead to early termination for efficacy or futility, is planned.

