6. EFFICACY ANALYSES

6.1. Primary Endpoint

6.1.1. Definition of the Primary Endpoint

The primary efficacy endpoint of this study is eGFR_{cr} slope from treatment-specific Baselines through Week 84. The values for eGFR_{cr} will be calculated using the CKD-EPI Creatinine Equation (2009):

$$eGFR = 141 \times \min\left(\frac{S_{cr}}{\kappa}, 1\right)^\alpha \times \max\left(\frac{S_{cr}}{\kappa}, 1\right)^{-1.209} \times 0.993^{Age} \times 1.018[\text{if female}] \times 1.159[\text{if Black}]$$

S_{cr} = standardized serum creatinine (mg/dL)

κ = 0.7 (females) or 0.9 (males)

α = -0.329 (females) or -0.411 (males)

min indicates the minimum of S_{cr}/κ or 1

max indicates the maximum of S_{cr}/κ or 1

age in years

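### As written, the first DMC safety review waits for the whole planned sample of about 300 to reach Week 12 or discontinue, too late to affect enrolment or run-in exposure to selonsertib

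*Protocol*

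**What the plan says.** Two passages set the timing of the first review.

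- Protocol 8.10: "The initial DMC meeting will occur after approximately 300 subjects reach Week 12 or discontinue from the study".
- SAP 2.1.1: "The initial review will be conducted after 300 randomized subjects have completed through Week 12 or discontinued from the study".

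The Protocol Synopsis gives the size of the study: "Number of Subjects Planned: Approximately 300 randomized subjects". The power calculation in Protocol 8.9.1 also uses 300 (150 per arm).

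On later meetings, Protocol 8.10 says: "Following this, subsequent meetings will occur approximately once every 6 months". It leaves membership, conduct and the meeting schedule to a charter. It lets the DMC recommend early termination, continuation or modification, and comment on study design.

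On efficacy, SAP 2.1.1 says: "No formal interim efficacy analysis, which may lead to early termination for efficacy or futility, is planned".

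Neither document names an earlier safety review or a calendar limit for the first one.

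**The concern.** A trigger equal to the full sample means that the DMC first sees data by arm when accrual is over. Any recommendation it makes on enrolment, eligibility or the run-in then has nobody left to protect.

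The run-in matters here because every subject takes SEL 18 mg for at least 4 weeks before randomization. Run-in treatment is open-label (Protocol 5.1), and other chemistry is collected and not listed as withheld. Run-in eGFR and serum creatinine, however, are kept from sites and sponsor, apart from eGFR below 15 and a flag for a decline of 50% or more (Protocol 6.4.12). eGFR is released from Week 4 (Protocol 1.3). After randomization, what is missing until the first review is an independent comparison of the arms.

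The Phase 2 data in Protocol 1.2.3.2.4 give some reason to want that comparison earlier. Serious adverse events occurred in 25.8% on pooled SEL and 18.8% on placebo. Acute kidney injury was reported in 7.2% on 18 mg and 2.4% on placebo. The counts are small and the protocol notes no dose-dependent toxicity. Still, SAP 7.1.7 lists cardiac failure and acute renal failure among the adverse events of interest.

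**Working it through.** **1. Is 300 the whole sample?** Inputs from Protocol 8.9.1: difference 3.7, SD 10, one-sided alpha 0.15.

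- 150 per arm: 3.7 / (10 × √(2/150)) = 3.204; power = Φ(3.204 − 1.036) = 0.985 (stated 99%).
- 127 per arm: 3.7 / (10 × √(2/127)) = 2.948; power = Φ(2.948 − 1.036) = 0.972 (stated 97%).

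Both agree with the stated figures to within a point, and a noncentral t calculation gives the same values. So 300 is the full planned sample, and the trigger is 300/300 = 100% of it.

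**2. When is the SAP trigger met?** With exactly 300 randomized, the last subject must reach Week 12 or discontinue. The trigger therefore lies between 0 weeks (immediate discontinuation) and 12 weeks (apart from the 5-day visit window) after the last randomization. A simulation with uniform accrual and an assumed 15% dropout per 48 weeks gave a median of 12.0 weeks. This step needs no accrual figure.

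**3. How long is accrual?** The documents do not say. SAP 6.1.3 and 6.2.2.3 plan slope analyses through Week 96. The Synopsis says: "The global study end date will occur when the last randomized subject reaches 48 weeks" (followed by an and/or clause). A subject can supply Week 96 data only if randomized at least 96 − 48 = 48 weeks before the last one. This suggests accrual of more than about 48 weeks. I also show 72 and 120 weeks as assumptions. The last is 168 − 48, from the final analysis window in SAP Table 3-2, which is a data-handling bin and only a soft ceiling.

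**4. Timing and exposure at the first review.** Assume uniform accrual over A weeks, 150 to SEL, no discontinuations, and a 5-week SEL run-in (visit windows allow 28 to 42 days).

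- First review = A + 12 weeks after first randomization.
- SEL patient-years = [150 × (12 + A/2) + 300 × 5] / 52.18.

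| A (weeks) | First review (week) | SEL patient-years |
|---|---|---|
| 48 | 60 | 6,900 / 52.18 = 132.2 |
| 72 | 84 | 8,700 / 52.18 = 166.7 |
| 120 | 132 | 12,300 / 52.18 = 235.7 |

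At A = 48, a 4- or 6-week run-in gives 126.5 or 138.0.

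**5. How many reviews fit?** If the first is at the last subject's Week 12, a 26-week interval puts the second at Week 38 and the third at Week 64. Only two fall before that subject's Week 48.

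**6. What would an earlier trigger change?** Take, for illustration, 75 to 100 randomized subjects at Week 12 or 26 weeks, whichever is earlier. At A = 48 accrual is 300/48 = 6.25 per week.

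- 75 subjects: randomized by week 12, at their Week 12 in week 24. Randomized so far 150; left 150.
- 100 subjects: randomized by week 16, at Week 12 in week 28, so the 26-week limit applies. Randomized 162.5; left 137.5.
- On run-in SEL at that moment: 6.25 × 5 = 31. Not yet started: about 119 or 106.
- SEL exposure in randomized subjects: (3.125 × t²/2 + randomized × 5) / 52.18 = 31.6 (t = 24) or 35.8 (t = 26) patient-years.

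At A = 72 or 120 the 26-week limit applies, and about 171 or 223 subjects would not yet have started SEL.

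**7. Does over-enrolment matter?** The plan is approximately 300. At a rate of 300/A, the trigger precedes the end of accrual only if the excess passes 12 × 300/A, that is 75, 50 or 30 subjects for A = 48, 72 or 120. With 309 randomized, the simulated median is still 10.6, 9.9 or 8.5 weeks after accrual ends.

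**The case against.** The strongest objection is the charter. Both documents leave the meeting schedule or frequency to it, and it may already provide an earlier review. That stands: the point concerns the two documents as written.

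A second objection is that a late first review may be reasonable given prior experience. Protocol 1.2.3 reports 248 DKD and 1,473 NASH subjects dosed and no adverse drug reactions identified. This lowers the urgency. It does not explain why the first review should wait for the full sample, and neither document offers that reasoning.

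Third, the exposure figures depend on unstated accrual. They assume no discontinuations although 15% dropout is planned, which overstates exposure. They omit run-in SEL in subjects never randomized, which understates it. They show scale only.

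Some stronger readings are tempting but not supported.

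- A reader might infer that safety goes unwatched until the first meeting. It does not: SAEs are reported within 24 hours (Protocol 7.3.2), sponsor pharmacovigilance may see group-level summaries (Protocol 5.1), and toxicity rules apply (Protocol 7.5). None of these is an independent review.
- A reader might infer that Protocol 8.10 contradicts the Synopsis, where the DMC "will meet regularly to evaluate all available safety data accumulated during the study". It does not: that sentence gives no start date, and six-monthly meetings after a late start are still regular.
- A reader might infer that with fewer than 300 randomized the SAP trigger is never met. That is too literal beside the protocol's approximate count.
- Protocol 8.10 does not say that its subjects are randomized, so a reader might count run-in discontinuations and put the trigger earlier. Week 12 is a post-randomization visit and no run-in failure rate is given, so no such timing can be worked out.

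**Conclusion.** The point holds for the wording of both documents, with high confidence. The first DMC safety review is tied to 100% of the planned sample. On the SAP count with 300 randomized it falls 0 to 12 weeks after the last randomization, so the first independent comparison by arm cannot affect enrolment or run-in SEL exposure.

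The size is conditional. Under the 48-week scenario the review comes about 60 weeks after first randomization and after about 132 SEL patient-years, and both grow with longer accrual. The practical consequence is less certain than the wording, because the charter could change it.

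This is a design choice that the sponsor should reconsider. It does not affect the validity of the primary analysis.

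**What to change.** Amend Protocol 8.10 and the charter so that the first safety-only review occurs when a fraction of the randomized sample reaches Week 12 or discontinues, or at a calendar limit after first randomization, whichever is earlier. An example is 75 to 100 randomized subjects or 6 months. These values are illustrative, do not come from the documents, and are for the sponsor and the DMC to set. Then continue about every 6 months as written.

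Count randomized subjects in both documents. Match SAP 2.1.1 for consistency; the operative timing sits in the protocol and charter. If the charter already provides an earlier review, the change is to bring the two documents into line with it.

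The cost is wording in three documents, a few extra DMC meetings and a few unblinded safety reports. The committee is already planned, and unblinded external statisticians are provided for in Protocol 5.1. There is no alpha cost, because the review covers safety only and no interim efficacy or futility analysis is planned.
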